#### 4.1.1.5 Overdose instructions

Symptoms of an overdose with hydroxychloroquine are headache, visual changes, seizures, hypokalaemia, cardiac arrhythmias (inclusive elongation of the QT-interval, Torsade de pointes, ventricular tachycardia, ventricular fibrillation) and cardiovascular failure. This can occur suddenly and can lead to death. As these symptoms can occur shortly after the overdose, an immediate medical treatment is necessary.

There exist no specific antidotes against hydroxychloroquine. In case of an overdose the stomach should be emptied by induced vomiting or gastric lavage. If the time point of overdose is less than 30 minutes ago, active coal - administered via gastric tube after the gastric lavage - can reduce further resorption of hydroxychloroquine. If necessary a support of pulmonary and cardiovascular function must be provided, e.g. adrenalin. Seizures have to be treated by benzodiazepines (diazepam), phenobarbital or if necessary by peripheral muscle relaxants and invasive ventilation. The cardiotoxicity of hydroxychloroquine can be reduced by the administration of parenteral diazepam. Haemodialysis is not suitable. Possibly a hypokalaemia has to be treated.

If the acute phase is over and the patient remains without any symptoms a strict monitoring for at least 6 hours is necessary.

(According to Fachinformation Quensyl®, January 2017)

For overdose instructions please refer also to the current country specific Summary of Product Characteristics of Hydroxychloroquinsulfate (SmPC).

#### 4.1.2 Placebo

Formulation: Mannitol, Maize starch, Silicon dioxide, Sucrose octaacetate, Sodium saccharine. Capsule

Manufacturer: University Hospital Munich, Pharmacy, [name], Germany.

Warnings and precautions for placebo capsules: Patients with hypersensitivity against one of the ingredients of placebo (see formulation) should not take the placebo capsules.

#### 4.1.3 Treatment assignment

The trial medication will be administered only to subjects included in this trial. Subjects withdrawn from the trial retain their identification codes. New subjects will always receive a new identification code.

#### 4.1.4 Treatment after the end of the trial

Treatment after the end of the trial is at the discretion of the investigator.

#### 4.1.5 Packaging and labelling

The trial medication will be labelled according to EU-GMP Annex 13.

The trial medication will be packed by pharmacy university medical centre Munich.

#### 4.1.6 Drug distribution to subjects

For all patients capsules with individual, body weight adjusted drug or placebo will be manufactured and shipped by the pharmacy within a week to the site for distribution to the patients or their caregivers. No adjustments of dose are necessary throughout the trial, as all patients will receive their body adjusted dose from the beginning.

#### 4.1.7 Drug storage, supplies and accountability

The investigator will take inventory and acknowledge the receipt of all shipments of the trial medication. All trial medication must be kept in a locked area with access restricted to designated trial staff. The trial medication must be dryly stored in accordance with manufacturer's instructions. The investigator will also keep accurate records of the quantities of trial medication dispensed, used, and returned by each subject on the drug accountability form. The site monitor will periodically check the supplies of trial medication held by the investigator to verify the correct accountability of all trial medication used. At the end of the trial, all unused trial medication and all medication containers will be disposed by the trial center according to the local regulations. It will be assured that a final drug accountability report is prepared and maintained by the investigator.

#### 4.1.8 Procedures for monitoring subject compliance

Trial medication will be dispensed to the subjects by the investigator. Subjects will be instructed to bring all trial medication to the trial site at every visit (including all empty packages and unused trial medication), compliance will be assessed. Details will be recorded in the CRF and on the drug accountability form in the investigator site file.

#### 4.1.9 Medication intake

Medication intake should take place with the meals or shortly after the meals.

These application forms are possible:

- Patients that can take the capsules:

Whole capsules will be taken with liquid (50-100ml water, tea or apple juice).

- Patient that can't take the capsules:

Capsules will be opened by the parents and content suspended in 5-20ml sweetened liquid (tea or apple juice) or taken with yogurt, jam, puree, apple sauce or pudding followed by liquid (50-100ml).

- Patient with feeding tube

Capsules will be opened and content suspended in 5-20ml water and immediately administered. After this tube will be flushed by additional 2.5-10ml water.

#### 4.1.10 Not permitted medication

Each previous and concomitant medication has to be documented in detail.

**Systemetic steroids:** pulsed glucocorticoids in the 4 weeks before entry into the study (day 1) and throughout the trail (V4 in START block and V6 in STOP block) are not allowed. A continous daily or alternate day oral dose of glucocorticoids is allowed and has to be stable in the 4 weeks before entry into the study (day 1) and throughout the trail.

Not permitted medication	Comedications very carefully to be considered (further explanation in the text)
Hepatotoxic medications, also caution with alcohol	Antiepileptics
Inhibitors of the monoaminooxidase	Digoxin
Arrhythmogenic medications	Cyclosporine
Amiodarone	Methotrexate
Moxifloxacin	Corticosteroids
Halofantrin	Aminoglycosides
Metronidazole	Agalsidase-beta
Phenylbutazon	Iaronidase
Probenecid	Neostigmine, Pyridostigmine
Indomethacin	Antacids
Penicillamin	Caolin
Pyrimethamine/Sulfadoxine	Cimetidine
Other medications that decrease the convulsive threshold	Praziquantel
Bupropion	Rabies vaccination with HDCV
Mefloquine	Insulin, antidiabetics
Other antimalarial	Ampicillin
	Azathioprin
	Other disease-modifying antirheumatic drugs

Due to an increased risk of ventricular arrhythmias the use of arrhythmogenic medication, as for example amiodarone or moxifloxacin, is not permitted during the trial. Halofantrin can prolong the QT interval with increased risk of arrhythmias and is therefore not permitted during the trial.

It is prohibited to use other hepatotoxic medication or inhibitors of the monoaminooxidase during the trial. Adolescent patients should be explained that no larger quantity of alcohol should be consumed during the treatment with HCQ.

The use of medication, that lowers the convulsive threshold, as for example mefloquine and bupropion, is not allowed during the trial, as there is an increased risk for seizures. The effect of antiepileptics can be reduced by hydroxychloroquine.

The use of digoxin and cyclosporine is not prohibited during the trial, but investigators must be aware that hydroxychloroquine may increase the plasma concentrations of digoxin and cyclosporine. So in this case a strict control of plasma-drug-level is necessary to avoid intoxication with digoxin or cyclosporine.

The use of other antimalarial drugs is not allowed during the trial because of a higher risk of side effects. With the use of phenylbutazon there is an increased risk for exfoliative dermatitis. If probenecid and indomethacin are used simultaneously there is an increased risk for sensibilisation and retinopathy. All three drugs are therefore not permitted during the trial.

The use of other disease-modifying antirheumatic drugs in patients who are already on the drugs is not prohibited during the trial, but the investigator must be aware of possible interactions and increased immunosuppression.

If hydroxychloroquine is combined with corticosteroids myopathies and cardiomyopathies can deteriorate. A combination with aminoglycosides leads to an increased neuromuscular blockade.

The combination with penicillamin can increase the risk for severe hematological and/or renal side effects and skin reactions. A combination with pyrimethamine/sulfadoxine increases the risk for skin reactions. Therefore these drugs must be avoided.

Simultaneous medication, which is toxic to the retina (e.g. tamoxifen) is not recommended.

Further, investigators must be aware, that hydroxychloroquine inhibits the effects of agalsidase beta (used in Fabrys disease), laronidase (used in mucopolysaccaridosis), neostigmine and pyridostigmine. It can also decrease the resorption of ampicillin.

In contrast, the effect of methotrexate is increased by hydroxychloroquine. Hydroxychloroquine can lead to an increased effect of antidiabetics (insulin, oral antidiabetics), so reduction of amount given can be necessary.

The effect of hydroxychloroquine can be reduced by caolin and antacids. If the use of antacids is necessary, there should be a time lag of 4 hours between the intake of hydroxychloroquine and antacids. The plasma concentrations of hydroxychloroquine can be increased by cimetidine.

Under the medication of the structural similar chloroquine-sulfate combined with metronidazole one acute dystonic reaction was observed, therefore the use of metronidazole during this trial is not permitted. The effect of praziquantel is reduced by chloroquine; so far it is not known if this is also the case with HCQ. In case of rabies vaccination with HDCV the production of antibodies can be reduced by HCQ.

(According to BSPAR guidance for hydroxychloroquine, October 2010 and Fachinformation Quensyl®, January 2017)

For interactions with other medications and further warnings and precautions please refer also to the current country specific Summary of Product Characteristics of Hydroxychloroquinsulfate (SmPC) for detailed information.

#### 4.2 Rescue medication or emergency treatment

There exists no special rescue medication in this trial. Children with interstitial lung disease often are very sick. So far we do not know which patient will benefit from the use of hydroxychloroquine and which will not. It is possible, that some patients will deteriorate during the trial. As no evidence based standards for treating interstitial lung disease in children exist, it is in the responsibility of the treating physician to decide, what the further treatment will be.

## 5 TRIAL SCHEDULE

Tables 1-1 and 1-2 on page 9 to 13 provide the detailed schedule of assessments during the trial, from the Screening Period through the last visit.

### 5.1 Ophthalmological review

Recommendation to consult ophthalmologist at baseline for baseline visual assessment and at the end of the initiation or withdrawal, including:

1. Enquiry about any disturbance of central vision
2. Check visual acuity and reading acuity
3. Slit lamp examination from age 3 years onward
4. Funduscopy

Facultative, not requested by the study physician and only at the discretion of the ophthalmologist

1. Ocular coherence tomography (OCT),
2. Fundus auto fluorescence (FAF) imaging
3. Stereoscopic slit lamp examination of the retina (e.g. with a 90D or 78 biconvex lens)
4. Central visual field, using an Amsler Chart (preferably red on black) or automated perimetry
5. Evaluation may need to be extended according to signs and symptoms to include retinal photography and visual electrophysiological tests.

**Subsequent examinations should be at the discretion of the ophthalmologist**, but indefinite follow up is not likely to be required for most patients. For patients who have received continuous treatment for more than 5 years, an individual arrangement should be agreed with the local ophthalmologist.

Visual side effects are dose related and the drug should be stopped if they develop.

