## Trial schedule

### START HCQ block

Table 1-1

Visit	Screening evaluations and Visit 1	Visit 2	Email-/Phone-Visit	Visit 3	Email-/Phone-Visit	Visit 4
Action	„Start of baseline“	“End of baseline“ + Day 1 of treatment	Every 7 days at home	End of 1 st Tx period	Every 7 days at home	“End of trial”
Trial day	-28 to -3	1	7, 14, 21 (+/- 3)	28 (-4, +7)	35, 42, 49 (+/- 3)	56 (-4, +7)
Demographics (e.g. sex, age)	X					
Patient information, informed consent	X					
Previous (last 12 months) and concomitant diseases	X	X	X	X	X	X
Previous (last 3 months) and concomitant treatments	X	X	X	X	X	X
Inclusion/exclusion criteria	X	X 				
Pregnancy test K	X*			X		X
Randomization a	X					
Trial medication supply to patient		X		X		
History (cardiotoxicity, hypoglycaemia)	X	X		X		X
Physical examination	X	X		X		X
Vital signs (BP, pulse, temp) b	X	X		X		X
ECG i	X*			X		X
Ophthalmologic review j	X*					X
Lab c (GOT/GPT/Crea/Potassium/CK/gGT/LDH/BB/DIFF / HCQ drug level, blood glucose)	X*			X		X
pO 2 , pCO 2 (capillary)	X	X 		X 		X 
O 2 -sat e , in room air	X	X	X	X	X	X
Respiratory rate, in room air	X	X	X	X	X	X
Retractions	X	X	X	X	X	X
Coughing	X	X	X	X	X	X
Oxygen demand	X	X	X	X	X	X
Chest x-ray	X 			X 		

CONFIDENTIAL

Visit	Screening evaluations and Visit 1	Visit 2	Email-/Phone-Visit	Visit 3	Email-/Phone-Visit	Visit 4
Pulmonary hypertension (Echo) j	X*					
Quality-of-life i	X*			X		X
Health Economics h	X*			X		X
Weight for height b	X*	X		X		X
Clinical course of lung disease	X 	X 	X 	X 	X 	X 
Exacerbation o	X 	X 	X 	X 	X 	X 
Adverse events	X	X	X	X	X	X
Drug accountability				X		X
Additionally in children > 5 years						
Spirometry / Bodyplethysmography a	X	X		X		X
6 minute walking distance (meter) g	X	X		X		X
O 2 -saturation before and after 6MWT	X	X		X		X
Borg scale t	X	X		X		X
Additionally in ventilated patients m						
Oxygenation index (OI) n	X	X	X	X	X	X
Duration (h) of mechanical ventilation	X	X	X	X	X	X
NO (%), ECLS (VV/VA/ECLA/Flow/time since insertion)	X	X	X	X	X	X

X\* Tests must be done before first drug dosing

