h Health economics assessment with the use of a special questionnaire which has to be filled out by the parents or adult patients.

i Quality of Life assessment with the use of the questionnaire PedsQL for different age groups which has to be filled out by parents and/or patients

j For Electrocardiography (ECG), ophthalmological review and Echocardiography (Echo) please see Chapter 5. If a routine ophthalmological examination was done within 3 month before Visit 1, no additional ophthalmological exam is required.

k Pregnancy test only has to be performed in girls of childbearing age and only if sexual relations are known or probable. It is at the discretion and responsibility of the attending physician to decide, whether a pregnancy test is necessary or not. The pregnancy test can be performed in the urine or serum.

l The following parameter will also be assessed, if there is **oxygen demand**:

1. O2 via nasal cannula or via face mask: O2-Flow (l/min)
2. on high-flow nasal cannula: Flow air (l/min), O2-Flow (l/min), FiO2

m The following parameter will also be assessed on ventilation: ventilation method, duration of ventilation (hours/day/only for non-invasive ventilation), PEEP (cmH2O), PIP (cmH2O), FiO2, Ti (sec), MPAW (cmH2O) and Oxygenation Index (OI);  
In addition, if patients on the heart lung machine (e.g. NO (%), ECLS (VV/VA/ECLA), Flow/time since insertion) will be documented descriptively.

n Calculation of Oxygenation Index (OI): OI = (FiO2 \* MPAW)/PaO2

with MPAW = ((frequency \* inspiration time)/60) \* ((inspiratory pressure (PIP) – PEEP) + PEEP)); If PaO2 is not available, PcapO2 can be used.)

o Start date, End date, Patient returned to baseline function? Y/N

1. Increase in respiratory rate? Y/N/not done.

2. Increase or development of dyspnea ? Y/N

3. Newly developing or increased abnormalities on chest imaging ? Y/N/not done

4. Onset/increase of oxygen demand to attain the individual baseline saturation ? Y/N

5. Need for an additional level of ventilatory support (in addition to oxygen) ? Y/N

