#### Summarized medical risk-benefit assessment:

In clinical practice HCQ is very frequently used in almost any patient with chILD at one or more occasions. Clear positive clinical improvements, usually occurring within 4 weeks, have been reported in 15 of 16 cases, when HCQ was given alone, and in 37 of 53 cases, when given in combination with glucocorticosteroids. Thus almost any child with a symptomatic form of chILD is treated with HCQ based on an empirical base.

The application, also for prolonged, uncontrolled periods over years, were obviously safe with very few, if any reported side effects during off-label usage. Of course a significant underreporting may be associated; however from other conditions and situations, in which the drug was used for a very prolonged time, including pregnancy and rheumatologic disease at significant higher frequency application was apparently safe and without major side effects even if given over a long period of time. Appropriate baseline testing (ophthalmologist, liver function values, blood count, electrolytes) is recommended before starting treatment to obtain baseline values. Subsequent examinations are at the discretion of the ophthalmologist, routine blood monitoring is not required.

Hydroxychloroquine may have potential for several side effects such as i.e. retinal changes and abdominal pain. The retinal changes are dose dependent and can be irreversible. In the 83 case reports of chILD that were treated with either chloroquine or hydroxychloroquine, there were only three cases in which retinal changes were reported. All three patients with retinal changes were treated with chloroquine over periods between 20 months and 9 years. In the case reports we retrieved, no retinal changes were reported in patients that received hydroxychloroquine. In one series of patients, who received hydroxychloroquine, abdominal pain in the first week of treatment with hydroxychloroquine was reported in a minority of cases. So the risk for major side effects seems to be much lower with the use of hydroxychloroquine instead of chloroquine. There are several case reports, where the patients received hydroxychloroquine safely over years.

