### 3.6.2 Exclusion criteria

Subjects presenting with any of the following criteria will not be included in the trial:

- chILD primarily related to developmental disorders
- chILD primarily related to growth abnormalities reflecting deficient alveolarisation
- chILD related to chronic aspiration
- chILD related to immunodeficiency
- chILD related to abnormalities in lung vessel structure
- chILD related to organ transplantation/organ rejection/GvHD
- chILD related to recurrent infections
- Acute severe infectious exacerbations
- Known hypersensitivity to HCQ, or other ingredients of the capsules (lactose-monohydrate, povidone, maize starch, magnesium stearate, hypromellose, macrogol or titanium dioxide (E 171), silicon dioxide or mannitol), to sucrose-octaacetate or sodium saccharine.
- Proven retinopathy or maculopathy
- Glucose-6-phosphate-dehydrogenase deficiency resulting in favism or hemolytic anemia
- Myasthenia gravis
- Hematopoetic disorders
- Pregnancy and lactation (Women with childbearing potential have to practice a medically accepted contraception during trial and till three months after the end of the treatment with HCQ, and a negative pregnancy test (serum or urine) should be existent on Visit 1, if girls of childbearing age and only if sexual relations are known or probable. It is at the discretion and responsibility of the attending physician to decide, whether a pregnancy test is necessary or not. Reliable contraception are systematic contraceptives (oral, implant, injection). Women that are sterile by surgery can participate in the trial. At the discretion of the investigator, sexual abstinence is also accepted as contraceptive method. Girls after menarche have to receive a counselling about birth control methods in presence of at least one parent, which has to be documented in the patient notes.)
- Participation in other clinical trials during the present clinical trial or not beyond the time of 4 half-lives of the medication used, at least one week.
- Hereditary galactose intolerance, lactase deficiency or glucose-galactose-malabsorption
- Renal insufficiency at screening, defined as glomerular filtration rate (GFR)
  - < 40 mL/min/1.73 m^2 in patients age 3 to 8 weeks
  - < 60 mL/min/1.73 m^2 in patients  $\geq$  8 weeks of age  
(KDIGO guideline 2012, K/DOQI guideline 2002)

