***Laboratory parameters (value, value normal/abnormal)**

Pregnancy test (male/female without childbearing potential yes/no, lactation period yes/no, pregnant yes/no, test performed yes/no, if test not done: reason)

ECG

Ophthalmological review (Visual acuity and reading acuity, Central visual field, using an Amsler Chart (preferably red on black) or automated perimetry, Slit lamp examination of the cornea, Stereoscopic slit lamp examination of the retina)

pO2, pcO2 (capillary)

**respiratory rate (b/min)*

**retractions*

**coughing*

**oxygen demand*

Chest x-ray scoring for chILD

Pulmonary hypertension (echo)

**measured at subsequent visits as well. Additionally in ventilated patients: Oxygenation index (OI), Duration (h) of mechanical ventilation, NO(%), ECLS (VV/VA/ECLA/Flow/time since insertion)*

*** measured at subsequent visits as well. Additionally in children >5years: FEV1% predicted (recorded in L), FVC% predicted (Recorded in L), 6 minute walking distance (meter), O2 sat before and after 6MWT, Borg scale*

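### Protocol 5.1 only recommends the eye review that the schedule makes mandatory, and the SAP omits its core retinal item and plans no post-baseline eye analysis

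*Protocol*

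**What the plan says.** **Protocol, status.** In Tables 1-1 and 1-2 the baseline ophthalmologic review carries the mark explained as "Tests must be done before first drug dosing". A second review stands at START Visit 4 (day 56) and at STOP Visit 8 (day 168). Footnote j then refers the site elsewhere: "For Electrocardiography (ECG), ophthalmological review and Echocardiography (Echo) please see Chapter 5". Section 5.1, the place it points to, opens with "Recommendation to consult ophthalmologist at baseline for baseline visual assessment and at the end of the initiation or withdrawal".

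**Protocol, waivers.** Footnote j continues: "If a routine ophthalmological examination was done within 3 month before Visit 1, no additional ophthalmological exam is required". Under Table 1-2, note X*8 allows a normal STOP Visit 8 examination to be reused for entry to START within 6 months, provided no HCQ was taken in between.

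**Protocol, content.** Section 5.1 has two lists. The core list holds an enquiry about central vision, visual and reading acuity, a slit lamp examination from age 3 years, and funduscopy. The other list is headed "Facultative, not requested by the study physician and only at the discretion of the ophthalmologist" and includes the stereoscopic slit lamp examination of the retina and the central visual field.

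**SAP.** Section 4.1 lists visual and reading acuity and central visual field, followed by "Slit lamp examination of the cornea, Stereoscopic slit lamp examination of the retina". Section 4.2.2 names the ophthalmologic review as a safety variable without giving components. The analysis text in 6.7.2 covers adverse events, laboratory values and vital signs, and its entry for other safety data is marked as not applicable.

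**The concern.** Protocol 4.1.1.3 calls change of vision the most important side effect of HCQ, and section 1.4 says that retinal changes can be irreversible. The eye review is the planned source of data on this, so three things should be settled: whether it is mandatory, when the second one takes place, and which variables are analysed.

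None of the three is settled. The schedule and the section it refers to give the examination different status. The SAP takes part of its variables from the optional list and leaves out the core retinal item. The second examination, the only one that could show a change on treatment, does not appear in the SAP schedules or in its analysis text. Following the SAP as written would give a baseline table with a partly filled retinal row and no planned summary of eye findings after baseline.

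**Working it through.** The documents give no figure on this point, so the check is a comparison of texts.

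**1. Content: protocol 5.1 against SAP 4.1**

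| Item | Protocol 5.1 | SAP 4.1 |
|---|---|---|
| Enquiry about central vision | core | absent |
| Visual and reading acuity | core | listed |
| Slit lamp | core, from age 3 years | listed, for the cornea |
| Funduscopy | core | absent |
| Stereoscopic slit lamp of the retina | facultative | listed |
| Central visual field | facultative | listed |
| OCT, fundus autofluorescence, extended tests | facultative | absent |

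The SAP carries 2 of the 4 core items, and 2 of its own 4 entries are facultative. Funduscopy is the only core item that is expressly retinal. The only retinal examination named in the SAP is the facultative one.

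**2. Status and timing**

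| Examination | Protocol 5.1 | Protocol Tables 1-1 and 1-2 | SAP schedules |
|---|---|---|---|
| Baseline | recommended | mandatory before first dose, subject to the waivers | marked as before first dose |
| Second, START | recommended, end of initiation | Visit 4, day 56 | none |
| Second, STOP | recommended, end of withdrawal | Visit 8, day 168 | none |

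In STOP, blinded withdrawal treatment ends at day 84 (Visit 5). If the end of withdrawal in 5.1 means that day, the scheduled examination comes 168 − 84 = 84 days, or 12 weeks, later.

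**3. What the SAP would do with the data**

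- The eye items stand among the baseline characteristics in 4.1, without the asterisk that marks variables measured again later.
- Section 6.2 summarises everything in 4.1 descriptively and adds exploratory between-group p-values.
- Section 5.1 of the SAP replaces no missing values. The retinal row would cover only patients who had the facultative test.
- Section 4.2.2 names the eye review as a safety variable, but 6.7.2 contains no analysis of it.

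Protocol section 8 says that the SAP is based on the protocol with all its amendments. The two documents should therefore agree on these items, and they do not.

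**The case against.** **The schedule probably governs.** Protocol section 5 says that Tables 1-1 and 1-2 give the detailed schedule. The waivers in footnote j and note X*8 make sense only if an examination is otherwise required. A reader might infer that children could be dosed without an eye examination, so that the exclusion "Proven retinopathy or maculopathy" would be applied unevenly. The documents do not support that as a consequence: it arises only if a site follows 5.1 against the table, and the SAP list has no bearing on eligibility. What stands is that footnote j sends sites to the weaker wording and no sentence says which text prevails.

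**Section 1.4 is not good evidence of a conflict.** A reader might cite "Subsequent examinations are at the discretion of the ophthalmologist, routine blood monitoring is not required". That sentence belongs to a paragraph on off-label use, and the trial does schedule blood tests after baseline. It reads as general practice and not as a trial rule.

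**Funduscopy is not strictly required.** Section 5.1 places it under a recommendation. It is a core-list item, and only the mark on the whole review makes that review mandatory.

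**How patients would be selected is not documented.** A reader might infer that testing follows signs, age or local habit. Section 5.1 ties only its fifth facultative item to signs and symptoms. The others rest on the ophthalmologist's discretion, with no stated criterion.

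**The STOP timing is ambiguous, not flatly contradictory.** Table 1-2 still labels days 126 and 154 as weeks of withdrawal, so the end of withdrawal can be read as day 168.

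**Few retinal events are likely in any case.** The protocol cites 2 cases in 400 patients (0.5%), both after 6 years of HCQ. At that rate, 80 complete examinations have a 1 − 0.995^80 = 33% chance of showing at least one event, and START treatment ends at day 56. This argues against any claim of a large loss of precision. It does not remove the need to report how many patients were examined and what was found. An abnormal finding could also appear as an adverse event, but adverse event tables do not separate patients examined and normal from patients not examined.

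**Conclusion.** The concern holds as a failure of the documents to agree, with a practical consequence for safety reporting. Three facts rest on the text alone: the eye review is recommended in one place and mandatory in another; the SAP omits 2 of 4 core items and relies on a facultative test for its only named retinal variable; and the SAP drops the second examination and specifies no analysis of a variable that it names as safety data. The last is the most consequential, because only the second examination can show change on treatment.

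No numerical size can be given. The share of patients who would have the facultative tests is not in the documents, and any precision or bias figure would depend on an invented share. The conclusion assumes only that the analysis follows the SAP as written. It does not extend to uneven eligibility. The sponsor should act on it before unblinding, since the repair is cheap and the data are already scheduled.

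**What to change.** 1. Reconcile protocol 5.1, Tables 1-1 and 1-2 with footnote j and note X*8, and the SAP schedules, so that all state one status for the eye review and one time point for the second STOP examination. The sponsor decides which.
2. In SAP 4.1, align the eye variables with the core list in protocol 5.1, including funduscopy (normal / abnormal / not done) and the central-vision enquiry. Put the facultative tests in a listing only.
3. Restore the second eye review to the SAP schedules. Add to SAP 6.7.2 a descriptive summary by arm of the eye review at baseline and at the second scheduled examination, with the number examined each time.

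The cost is wording in both documents and one extra table. No examination is added to those already scheduled.
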